Protocol ID: 1708785351

ClinicalTrials.gov ID: NCT03435835

Date of document: 01/28/2022

Official Title: Heat Therapy to Reduce Leg Pain and Improve Walking Tolerance in Patients
With Symptomatic Peripheral Artery Disease

STUDY PROTOCOL AND STATISTICAL ANALYSIS PLAN

Experimental Design

A schematic of the experimental protocol is depicted in Figure 1. To familiarize participants with the symptom-limited cardiopulmonary treadmill exercise test and assess the test-retest reliability of walking tolerance, two tests were completed at baseline, at least 72 hours apart. On visit 1, participants underwent a lower extremity arterial examination to determine the ankle-brachial index (ABI). Next, participants were escorted to an adjacent room and underwent resting pulmonary function testing, followed by a graded cardiopulmonary treadmill exercise test. Pulmonary oxygen uptake ($\dot{V}O_2$) and calf muscle oxygenation were measured continuously throughout the test. Similar procedures were followed on visit 2, with the exception of the lower extremity arterial exam. If the difference in peak walking time (PWT) during the exercise tests between visits 1 and 2 was greater than 20%, participants were asked to complete a third exercise test, at least 72 hrs after visit 2. Once the variation in PWT was deemed acceptable (i.e. <20%), participants were assigned, using a randomized, crossover design, to undergo a single session of either HT or a control treatment (CON) prior to a symptom-limited cardiopulmonary treadmill exercise test. The primary study outcome was the difference in peak walking time (PWT) between HT and the CON conditions. Secondary outcomes included the differences between visits in claudication onset time (COT), blood pressure and calf muscle oxygenation at rest and during exercise, pulmonary oxygen uptake ($\dot{V}O_2$) and plasma ET-1, IL-6 and TNF-a concentrations post-treatment and post-exercise. Prior to the experimental visits, participants were asked to report to the laboratory in a fasted state (>8 hrs postprandial), refrain from exercise (24 hrs), smoking (>4 hrs), and take their usual medications.

Pulmonary function tests

Pulmonary function tests were performed following the American Thoracic Society and European Respiratory Society guidelines ¹. FVC and FEV1 were measured and reported as both raw and %predicted values ².

Symptom-limited cardiopulmonary exercise test

Exercise testing was performed in a motorized treadmill (Pro 27, Woodway, St. Paul, Minnesota, United States) following the Gardner-Skinner protocol, which consists of walking at a constant speed (2 mph) with a 2%-grade increase every 2 min ³. A 12-lead electrocardiogram (ECG) was registered continuously. Blood pressure was measured in the left arm using a stethoscope and sphygmomanometer prior and during exercise and for 10 min during recovery. Expired respiratory gases were collected breath-by-breath via a facemask attached to a gas analyzer (MedGraphics, CardiO2, and CPX/D system using Breeze EX Software, 142090-001, ReVia; MGC Diagnostics, St. Paul, MN, United States). Calf muscle oxygenation was assessed using a near infrared spectroscopy device (NIRS; Portomon, Medis, the Netherlands), which was affixed on the skin over the medial portion of the gastrocnemius of the leg of which the participants self-described as having the more severe pain during exercise. Participants received standardized instructions and were asked to indicate when they first began to feel leg pain with a “thumbs up” signal (defined as COT), and then give a “thumbs down” signal when they could no longer continue with the test (defined as PWT). Participants were allowed to use the handrails for balance, but were not allowed to use them as an aid for walking (i.e. pulling themselves up).

Heat and control treatments

Participants were instructed to ingest a core temperature sensor (CorTemp, HQ Inc., Palmetto, Florida, United States) the night before the experimental visits. Upon arrival, participants were allowed to rest for 15 min and were then instrumented with leg skin thermistors (MLT422; ADInstruments, Colorado Springs, CO, United States) and a blood pressure cuff on the upper arm that was connected to an automated monitor (Suntech CT40, Suntech Medical, Morrisville, North Carolina, United States). An intravenous catheter was placed in an antecubital vein of the left arm for blood sampling. After 30 min of rest in the semi-recumbent position, participants were fitted with liquid-circulating trousers as described previously ⁴. In the CON session, water at 33°C was circulated through the trousers for 90 min using a water pump (HTP-1500, Adroit Medical, Louden, Tennessee, United States). We have previously demonstrated that this regimen elevates skin temperature by approximately 2°C, but does not evoke measurable changes in core body temperature, heart rate and blood pressure ⁴. In the HT session, water at 43°C was circulated through the tube-lined trousers using a heated bath circulator (HT; Aqua Relief Systems, Akron, Ohio, United States) with the goal of increasing leg skin temperature to 37-38°C. The following parameters were assessed every 5 min during baseline and throughout the 90-min intervention: intestinal temperature (HQ Inc., Palmetto, Florida, United States), leg skin temperature, blood pressure, and heart rate. Prior to the onset of the treatment and at 45 and 90 min, patients were asked to subjectively grade thermal comfort scores using an 11-point feeling scale ⁵. After the completion of the treatment, participants were promptly escorted to an adjacent room and performed a symptom-limited exercise test as in visits 1 and 2. Blood samples were taken at baseline, at the end of the 90-min treatment and 10 min after the end of the exercise test.

Assessment of tissue oxygenation

The tissue saturation index (TSI%) of the most symptomatic leg was assessed with a commercially available NIRS system (Portamon, Artinis Medical Systems, The Netherlands). Initially, the skin over the medial gastrocnemius of the most symptomatic leg was cleaned and, if necessary, shaved. The device was affixed using medical tape and covered with a dark cotton sleeve. The location of the monitor was traced with permanent marker to ensure consistent placement in subsequent visits. The tracings were covered with an adhesive dressing (Tegaderm, 3M, Maplewood, MN, United States) after the exercise test and re-drawn at each subsequent visit. Data were exported at 1Hz and the final 20-second average of each stage was utilized for analysis.

Analysis of blood markers

Samples were drawn into tubes containing EDTA (BD Vacutainer, BD, Ontario, Canada). One tube was transported to the Indiana University Health Pathology Laboratory for the assessment of a routine basic metabolic panel. All other plasma samples were centrifuged at 4°C for 10 min at 1,100 g (ST16, Thermo Scientific, Waltham, MA, United States). Samples were then aliquoted and immediately placed into a -80°C freezer. Commercially available enzyme-linked immunosorbent assay kits were used to measure the plasma concentrations of ET-1 (DET100, Endothelin-1 Quantikine ELISA Kit, R&D Systems, Minneapolis, MN, United States), TNF- α (HSTA00E, Human TNF-alpha Quantikine HS ELISA kit, R&D Systems, Minneapolis, MN, United States) and IL-6 (HS600C, Human IL-6 HS ELISA Kit, R&D Systems, Minneapolis, MN, United States). Blood biomarker values were corrected for potential changes in plasma volume during heating and exercise as described elsewhere ⁶.

Statistical Analysis

All data were analyzed using SAS v9.4. Data are presented as mean \pm SD. Variables assessed during exposure to HT or CON (blood pressure, intestinal temperature, HR, and skin temperature) were compared using a two-way repeated measures analysis of variance (ANOVA). PWT and COT times were compared using a paired t-test. All measurements taken at COT and PWT were time-aligned (isotime) between visits 3 and 4 at the point of the earlier COT and PWT. Blood pressure during exercise was compared between groups using a two-way repeated measures ANOVA. Missing values during the exercise test were imputed by linear interpolation, using the mean of the values from the two adjacent stages. If the value for the final stage was missing, then it was recorded as a repeat of the previous stage. TSI% and $\dot{V}O_2$ are represented using the mean of the final 20 seconds for each stage. Staged averages were compared using a two-way repeated measures ANOVA. When a group-by-time interaction was detected, post-hoc analysis compared values at each time point. A Bonferroni adjustment was applied to correct for multiple comparisons when appropriate.

REFERENCES:

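### Does using the left arm for both exercise blood pressure and the sampling catheter undermine the post-exercise biomarkers?

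*Combined protocol and SAP*

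**What the plan says.** Under *Symptom-limited cardiopulmonary exercise test*: "Blood pressure was measured in the left arm using a stethoscope and sphygmomanometer prior and during exercise and for 10 min during recovery". The position of the cuff on the arm and the times of the recovery readings are not given.

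Under *Heat and control treatments*, for the experimental visits: "An intravenous catheter was placed in an antecubital vein of the left arm for blood sampling". After treatment the participants "performed a symptom-limited exercise test as in visits 1 and 2". On timing: "Blood samples were taken at baseline, at the end of the 90-min treatment and 10 min after the end of the exercise test". During treatment there was also "a blood pressure cuff on the upper arm that was connected to an automated monitor"; its side is not given.

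*Experimental Design* lists among the secondary outcomes the differences between visits in blood pressure and in "plasma ET-1, IL-6 and TNF-a concentrations post-treatment and post-exercise". *Analysis of blood markers* adds: "Blood biomarker values were corrected for potential changes in plasma volume during heating and exercise as described elsewhere". *Statistical Analysis* says: "Blood pressure during exercise was compared between groups using a two-way repeated measures ANOVA". It names no test for the three plasma markers.

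**The concern.** Inflating a cuff upstream of a sampling line can briefly hold back venous return or disturb the line, and a catheter at the elbow can get in the way of the stethoscope. It is therefore natural to put the two on opposite arms. Here both are on the left, and nothing in the text moves either device for the HT and CON visits. The recovery blood pressure window also lasts 10 min, the same interval that precedes the last blood draw, so a reading could come just before the sample.

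At stake would be the precision of the post-exercise ET-1, IL-6 and TNF-alpha comparisons and, by a different route, the accuracy of auscultated blood pressure during exercise. All are secondary outcomes. Separating the devices would also have cost nothing, which makes the arrangement look like an oversight.

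**Working it through.** The plan gives no figure on this point to reproduce: no biomarker SD, sample size or number of cuff readings. The check is therefore mainly a comparison of the sections.

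**1. Do the sections put both devices on one arm?** Yes, as written. The exercise-test section names the left arm for manual readings, the treatment section names the left arm for the catheter, and the experimental exercise tests follow the procedure of visits 1 and 2. The carry-over is by a general phrase, from visits for which no catheter is described.

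**2. How much is exposed?** There are 3 samples per experimental visit: baseline, end of treatment and post-exercise. Only the last follows the stated left-arm exercise readings, so 1 of 3. With 3 markers at 2 reported time points there are 3 × 2 = 6 marker-by-time differences, of which 3 are post-exercise. These count exposure, not bias. If the automated cuff was also on the left, all 3 samples would be exposed; the text does not say.

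**3. How close are the last reading and the draw?** Let the last recovery reading come t minutes after walking stops, with 0 < t ≤ 10.
- If the test ends when walking ends, the draw is at 10 min and the gap is 10 − t, that is 0 to under 10 min.
- If the test includes the 10-min recovery, the draw is at 20 min and the gap is 20 − t, that is 10 to under 20 min.

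The definition of peak walking time, the point at which the participant cannot go on with the test, favours the first reading. Even then, the order of the last reading and the draw is open, and drawing first would avoid that inflation.

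**4. What must be true for harm?** The manual cuff was on the upper arm; the catheter stayed in through treadmill walking; the last sample came from it; a reading came shortly before the draw; and the disturbance was large enough to show in the assay. The documents state none of these.

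**5. What would it do to the comparison?** The outcome is a within-participant difference. For a constant effect c on the sample:

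(HT + c) − (CON + c) = HT − CON, so the change is 0.

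For independent random noise whose SD in the HT-CON difference is k times the existing SD of that difference, the standard error is multiplied by √(1 + k²):
- k = 0.25: √1.0625 = 1.03
- k = 0.5: √1.25 = 1.12
- k = 1: √2 = 1.41

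These k values are assumptions. The result runs from trivial to substantial according to a quantity the documents do not give, so the formula says nothing about this trial. Noise that did occur is already part of the spread of the observed differences, and hence of any standard error computed from them.

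**6. What can still be altered?** Procedures and analysis alike are described in the past tense, in a document dated 01/28/2022. No session is shown as still to be run.

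**The case for a change.** The best case for acting is that the facts are plain and the remedy is nearly free. Both sections name the left arm, no minimum gap between cuff deflation and draw is set, and the plasma-volume correction is described for heating and exercise, with nothing to show that it covers a local effect in the sampled arm. Cancellation also needs the effect to be equal in the two conditions. If participants walked longer after heat, they may have had more cuff inflations in that session.

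The reading of the text stands, and so does the caveat that equal effects are assumed, not shown. The plasma-volume correction can be used by neither side, because the cited method is not reproduced in the document.

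What does not stand is the step to a needed change. The mechanism is plausible in general, but the documents neither state nor size it for this trial. Swapping arms helps only in sessions still to come, and none is documented. What remains is a sentence on which arm carried which device and in what order the last reading and draw were taken. That is useful to a reader of the results, but it alters no data, test or estimate.

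**Conclusion.** The shared left arm is real on the page, but it does not call for a change to the plan. It is a set-up preference with an unstated detail: the sections are compatible, and any harm depends on several unstated conditions.

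The exposure is 1 of 3 samples per experimental visit, assuming an upper-arm manual cuff and a catheter left in place, and leaving aside the automated cuff. The size of any effect is unknown and could be nil. If it was similar under HT and CON, it drops out of the difference apart from some added noise in three secondary markers. Exercise blood pressure could be affected only through harder auscultation, which the documents do not report. Peak walking time and claudication onset time do not depend on the cuff or the catheter.

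With data collection and analysis described as done, moving a cuff would gain nothing. The investigators can name the arms and the order of the last reading and the draw when they report the biomarkers, and note the shared arm as a limitation if it was shared.

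### The paired t-test for PWT (primary) and COT ignores period in a two-session randomised crossover; report a period-adjusted HT-CON difference with the numbers per sequence.

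*Combined protocol and SAP*

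**What the plan says.** Experimental Design states that "participants were assigned, using a randomized, crossover design, to undergo a single session of either HT or a control treatment (CON") before a treadmill test, and that "The primary study outcome was the difference in peak walking time (PWT) between HT and the CON conditions". COT is listed there as a secondary outcome. Statistical Analysis shows that the two sessions are visits 3 and 4, since exercise measurements are "time-aligned (isotime) between visits 3 and 4". For PWT and COT the whole stated analysis is: "PWT and COT times were compared using a paired t-test".

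The repeated measures ANOVAs in the same section are assigned to other variables, and the interaction they refer to is group by time. Nowhere do the documents give a period or sequence term, a period-adjusted sensitivity analysis, the randomisation method, or the number of participants in each order.

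Before randomisation, "two tests were completed at baseline, at least 72 hours apart", partly for familiarisation. If PWT differed by more than 20%, "participants were asked to complete a third exercise test, at least 72 hrs after visit 2".

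**The concern.** A paired t-test pools all HT-CON differences as if order did not matter. If PWT tends to be longer or shorter at visit 4 than at visit 3 whatever the treatment, that shift enters the differences with one sign in participants who had HT first and the opposite sign in those who had CON first. With equal sequences it cancels from the mean but stays in the variance, which widens the interval and costs power. With unequal sequences part of it also remains in the estimate.

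PWT is symptom-limited and ends on the participant's own signal. The design itself anticipates change on repeat testing, since it includes familiarisation tests. At stake is whether a reader can tell if the primary result was blurred or moved by session order. With neither a period term nor the split, that cannot be judged.

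**Working it through.** The plan has no figure to reproduce: it states no sample size, SD, target effect, alpha, period effect or split.

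**Assumptions, for illustration only:** n = 16; SD of within-person HT-CON differences σ = 15% of PWT; HT effect τ = 10%; two-sided alpha 0.05; period effect π (visit 4 minus visit 3) from 0 to 15%. Let n1 be the number with HT first and n2 the number with CON first.

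**Model.** The HT-CON difference has mean τ − π in HT-first participants and τ + π in CON-first participants. Then:
- Bias of the paired mean = π(n2 − n1)/n.
- Expected sample variance = σ² + 4π²·n1·n2/[n(n − 1)]; at 8:8 this is 225 + π²·16/15.
- Period-adjusted estimate = average of the two sequence means, with SE = (σ/2)·√(1/n1 + 1/n2) on n − 2 df.

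Rejection rates for the paired test come from the exact doubly noncentral t distribution; adjusted power comes from the noncentral t.

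**Equal sequences (8:8), τ = 10%.** The paired half-width is 2.131·√(225 + π²·16/15)/4. The adjusted half-width is 2.145·15/4 = 8.0 points.

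| π (% of PWT) | Paired power | Adjusted power | Paired 95% CI half-width (points) |
|---|---|---|---|
| 0 | 70% | 70% | 8.0 |
| 5 | 66% | 70% | 8.5 |
| 10 | 54% | 70% | 9.7 |
| 15 | 37% | 70% | 11.5 |

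**Other sample sizes, equal sequences, paired against adjusted power:**
- n = 12: 51% v 55% at π = 5; 39% v 55% at π = 10.
- n = 20: 77% v 80% at π = 5; 67% v 80% at π = 10.
- n = 24: 85% v 88% at π = 5; 77% v 88% at π = 10.

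**No treatment effect (τ = 0), n = 16.** Example of the bias: at 6:10 with π = 10, 10 × 4/16 = 2.5 points.

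| Split | Bias, π = 10 | Paired type I error, π = 5 | Paired type I error, π = 10 |
|---|---|---|---|
| 8:8 | 0 | 3.9% | 1.9% |
| 7:9 | 1.25 | 4.2% | 2.6% |
| 6:10 | 2.5 | 5.0% | 4.6% |
| 5:11 | 3.75 | 6.3% | 8.7% |
| 4:12 | 5 | 8.3% | 15.5% |

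**How often such splits arise.** Under simple 1:1 randomisation of 16, splits at least as unequal as 6:10, 5:11 and 4:12 occur 45%, 21% and 8% of the time. Averaged over all splits, the bias is zero and type I error is 5.0%.

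**When adjustment pays.** At an unequal split the adjusted estimate has the smaller mean squared error once π exceeds √(Var_adj − Var_paired) ÷ [(n2 − n1)/n]. At 6:10 this is √(15.00 − 14.06)/0.25 = 3.9. Over splits from 7:9 to 4:12 it runs from 3.8 to 4.3% of PWT.

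**The case against.** The strongest reply is that the planned test is sound for this design. Order is randomised, so over simple randomisation the estimate is unbiased and type I error is 5%; with equal sequences the test is at worst conservative. The design already acts against learning through two or three familiarisation tests, and nothing in the documents shows a shift between visits 3 and 4. For small shifts adjustment does not pay: averaged over simple randomisation at n = 16, paired against adjusted power is 70% v 67% at no shift, 69% v 67% at 3%, about level at 4%, and 66% v 67% at 5%. The clear gain (54% v 67%) needs a 10% shift, which is pessimistic after familiarisation. The type I errors of 8.7% and 15.5% need both that shift and a markedly uneven split, which blocked allocation, neither stated nor excluded, would make rarer.

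All of this stands, and it limits the severity. It does not close the gap. The 20% rule limits one person's test-to-test variation before randomisation; it neither measures nor removes a mean shift between visits 3 and 4. A test that is right on average over possible splits also does not tell a reader whether the split actually obtained moved this estimate.

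**Conclusion.** The concern holds. The only stated analysis of the primary outcome, and of COT, omits a period term in a two-period randomised crossover, and nothing else in the documents supplies one. This is not an invalid test. It is a possible loss of precision, plus a bias that depends on a split the documents do not give.

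Under the assumptions above, a 5% shift at equal sequences costs about 4 points of power, and a 10% shift about 16. Inflation of type I error above 5% needs a split of about 5:11 or worse at n = 16. These figures depend on the assumed n, SD, effect and shift; the algebra does not. A period-adjusted result is a worthwhile, inexpensive improvement rather than a correction of a demonstrated error.

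**What to change.** Analyse PWT and COT with a linear mixed model (PROC MIXED in the SAS release already named) with fixed treatment, period and sequence and a random participant effect, or use the equivalent Hills-Armitage comparison of period differences between sequences. Report the period-adjusted HT-CON difference with its 95% CI, the period estimate, and the number of participants per sequence. The text is in the past tense, so if the paired analysis has already been run, keep it and place the period-adjusted result beside it, labelled as an added analysis.

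The work is one sentence in Statistical Analysis and a few lines of code, with no new data. It is not free. With no period effect at n = 16, power goes from 70.3% to 69.9% at 8:8, and from 70% to 67% (6:10), 63% (5:11) or 58% (4:12). Period adjustment does not address carryover between the two sessions.

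### Filling a missing final-stage exercise value with the lighter previous stage biases the final-stage heat-versus-control difference in secondary measures if missingness differs between sessions

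*Combined protocol and SAP*

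**What the plan says.** The Statistical Analysis section gives two fill rules for gaps in the exercise data. For inner stages: "Missing values during the exercise test were imputed by linear interpolation, using the mean of the values from the two adjacent stages". For the end of the test: "If the value for the final stage was missing, then it was recorded as a repeat of the previous stage". Exercise blood pressure and the stage averages of tissue saturation (TSI%) and oxygen uptake (VO2) then go into two-way repeated measures ANOVAs, with stage-by-stage comparisons if an interaction is found.

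Three other statements bear on this:

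- The section on the symptom-limited exercise test describes "walking at a constant speed (2 mph) with a 2%-grade increase every 2 min", so no two stages have the same workload.
- The same section says "Blood pressure was measured in the left arm using a stethoscope and sphygmomanometer prior and during exercise". The test ends when the participant gives the stop signal, not at a fixed time.
- The Statistical Analysis section also says: "All measurements taken at COT and PWT were time-aligned (isotime) between visits 3 and 4 at the point of the earlier COT and PWT".

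Experimental Design lists "blood pressure and calf muscle oxygenation at rest and during exercise" among the secondary outcomes. The documents give no missing counts, no change per stage, no sample size, and no sensitivity analysis for the fill rules.

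**The concern.** The inner-gap rule is unbiased when a measure changes linearly across stages. The final-stage rule is not: it replaces a reading at the heaviest workload with one taken 2 grade points lower, and the ANOVA treats the copy as data. For a measure that rises with grade, each filled value is on average too low by one stage's rise. If this happens more often in one session, part of the workload effect is booked as a treatment effect at the final stage. Because comparisons are made by stage after an interaction, that contrast can be reported.

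Exercise blood pressure is the measure most exposed. It is read by manual cuff in a test that the participant may stop at any moment, so the last reading may be the one missed (an inference; the documents do not say so). The plan does not say clearly whether the rule also covers TSI% and VO2. Both were recorded continuously and averaged over the last 20 seconds of a stage, so gaps there should be rare.

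The wording is also open on two points: whether the final stage is each session's own last stage or the aligned (isotime) one, and whether filling came before alignment.

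**Working it through.** **No figure to reproduce.** The plan states no number on this point, so every input below except the grade step is an assumption.

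**1. Formula.** Let g be the true change from the previous to the final stage and m the share of final-stage values missing, unrelated to the values. The filled final-stage mean is

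(1 - m)(previous + g) + m(previous) = previous + g - m·g.

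The HT-CON difference therefore shifts by -(m_HT·g_HT - m_CON·g_CON). With equal g this is -g(m_HT - m_CON).

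**2. Unequal missingness, no true effect, g = 10 mmHg.**

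- 30% vs 10%: -10 × 0.20 = -2.0 mmHg (-1.0 at g = 5, -3.0 at g = 15)
- 20% vs 10%: -10 × 0.10 = -1.0 mmHg
- 10% vs 5%: -10 × 0.05 = -0.5 mmHg

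The sign reverses if CON has the more missing values. If a participant stops partway and would have shown only half the stage's rise, these figures halve.

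**3. Equal missingness.** With the same effect at the last two stages, g_HT = g_CON and the shift is 0. With an effect d confined to the last stage, g_HT = g_CON + d, the shift is -m·d, and the estimate is (1 - m)d. At m = 20% and d = 5 mmHg this is 0.8 × 5 = 4.0 mmHg.

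**4. Isotime reading.** Suppose the final stage means each session's own last stage and filling comes first. At the last shared stage, the shorter session is then carried forward and the longer one interpolated. With equal missing share m, the shift is m·g × (share with CON shorter - share with HT shorter). At m = 20% and CON shorter in 90%, it is 0.20 × 10 × (0.9 - 0.1) = +1.6 mmHg. At 50% it is 0.

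**5. Simulation.** Assumed: n = 16, participant SD 12, session SD 6, residual SD 8 mmHg, linear rise, no true effect.

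With the planned two-way ANOVA and everyone ending at stage 5, the shifts were -2.0, -1.0 and -0.5 mmHg for the three missing patterns in step 2. At 30% vs 10% the interaction test rejected in 7.0% of trials, against 5.1% with complete data. The 5 mmHg last-stage effect in step 3 came out as 4.0.

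With the last shared stage at 4, 5 or 6 (equally likely), a classical ANOVA needs the same stages for everyone. Filled and observed-only data were therefore both fitted by a mixed model with stage as actual grade (3,200 trials per row; simulation error of a rate about 0.4 to 0.5 points):

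| Missing HT/CON | Rise per stage | Shift with fill, stages 4/5/6 (mmHg) | Interaction error, fill | Interaction error, observed only |
|---|---|---|---|---|
| 30%/10% | 10 | -0.7/-1.0/-2.2 | 6.5% | 5.5% |
| 30%/10% | 15 | -1.1/-1.8/-3.5 | 8.3% | 5.5% |
| 30%/10% | 5 | -0.4/-0.5/-1.1 | 4.7% | 4.6% |
| 20%/10% | 10 | -0.3/-0.6/-0.9 | 5.8% | 4.9% |

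The observed-only shift was within 0.15 mmHg in every row. In the first row, the shift at each participant's own last shared stage was -2.0 mmHg. At n = 24 in that setting, the error was 7.0% with fill and 4.7% without. Stages reached in only one session were not simulated.

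**6. Scale.** Under these SDs, the complete-data standard error of the paired difference at one stage is √[2(6² + 8²)/16] = √12.5 = 3.5 mmHg. Shifts of 2.0, 1.0 and 0.5 mmHg are about 0.57, 0.28 and 0.14 of it.

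**The case against.** The strongest reply is that nothing in the documents shows final-stage missingness to differ between sessions. The same test follows either treatment, and a manual cuff with a participant-ended test is common to both. At an assumed n of 16, 30% vs 10% means roughly 5 versus 2 lost readings, which is a wide gap; milder gaps move the estimate by 0.5 to 1.0 mmHg. The test error barely moves in most scenarios: 6.5% against 5.5% is within about 1.7 simulation standard errors. Only secondary measures are touched. The plan is written in the past tense, so replacing the main analysis now would be post hoc.

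Much of this stands. The size is probably small, the direction cannot be known from the documents, the scope is essentially exercise blood pressure, and any added model must be labelled as such. Two things do not follow. First, equal missingness is not fully protective: an effect confined to the last stage is still diluted. Second, the trial asks whether heat changes walking time. If it does, the two sessions may end at different points, and unequal loss of the last reading is then plausible, though not shown. The missing counts that would settle this are not given.

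**Conclusion.** The concern holds, conditionally. The final-stage rule puts a lighter-workload value in place of the heaviest one. For any measure that changes with grade, this biases the final-stage HT-CON difference whenever missing shares differ between sessions. The shift is a fraction of one stage's change: 0.5 to 2.0 mmHg in size for the missing patterns examined at an assumed rise of 10 mmHg, and 3.0 by formula (up to 3.5 at one stage in simulation) at a rise of 15 with 30% vs 10% missing. Significance testing is clearly affected only with a wide gap in missingness and a rise of 10 mmHg or more per stage. The sample size, SDs, rises and missing rates are all assumed. The primary comparison of peak walking time and the comparison of claudication onset time are untouched. The change is worth making because a better analysis of the same data costs little; the trial's main conclusion does not depend on it. Confidence is medium, because the true missing counts are unknown.

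**What to change.** Analyse the staged exercise measures with a REML mixed model (PROC MIXED) on observed values only. Fixed effects: treatment, stage as actual treadmill grade, treatment-by-stage and period. Random effects: participant and participant-by-session. The period term is not needed to cure this fault but suits a crossover. Keep the two fill rules as a sensitivity analysis, and state the missing-at-random assumption.

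Also report missing counts by condition and stage, and state what the final stage means, whether filling came before or after isotime alignment, and whether the rules cover TSI% and VO2. If results under the fill rules already exist, report the model beside them and label it as added later.

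The cost is SAP wording and a few lines of SAS on data already collected. Estimated standard errors widen where values are missing. In the 30% vs 10% simulations:

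- All ending at one stage: 3.90 vs 3.71 (about 5%).
- Unequal lengths, stage 5: 4.40 vs 4.25 (4%).
- Unequal lengths, stage 6: 6.60 vs 5.84 (13%); only about a third of participants reach this stage.
- Averaged over last shared stages: 3.41 vs 3.21 (6%), although the true sampling spread was the same (3.43 vs 3.42).

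The model is not a full cure if missingness depends on the unseen value. With the odds of missing multiplied by 2.7 per SD of that value, it kept shifts of -0.1, -0.3 and -0.7 mmHg at stages 4, 5 and 6, against -0.7, -1.2 and -2.3 for the fill rule.
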